2. BACKGROUND INFORMATION

Multiple sclerosis (MS) is an autoimmune, inflammatory, demyelinating disease of the central nervous system (CNS) influenced by genetic susceptibility and some environmental factors not yet fully understood³. Relapsing forms of MS (RMS) are generally characterized by clearly defined periods of worsening neurological symptoms [i.e. relapse] followed by full or partial recovery [i.e. with sequelae and residual deficits upon recovery]. Relapsing forms of MS

include relapsing remitting or secondary progressive. In RMS, there is no clinically obvious disease progression during the periods between disease relapses⁴.

Relapses are typically treated with a high dose of glucocorticoids over a short period of time [3-5 days]. Certain immunomodulatory agents, including interferon beta preparations, glatiramer acetate, natalizumab, fingolimod, dimethyl-fumarate, alemtuzumab and teriflunomide, have shown beneficial effects for patients with RMS (decreased relapse rate and a slower accumulation of brain lesions on MRI). However, these treatments may be associated with significant toxicity and limited efficacy over time⁴.

2.1.Pathophysiology of Multiple Sclerosis and gut bacteria

The gut microbiome has recently emerged as a potential contributor to MS pathogenesis^{5,6}. Previously reviewed data from murine model of autoimmune demyelinating disease^{7,8} suggest that gut microbiota can powerfully modulate immune-mediated demyelination. Moreover, studies involving MS patients have shown that their microbial composition is different compared to healthy controls^{9,10,11} and this could be related to disease development and activity¹². Fecal microbial transplantation (FMT) from healthy donors is already used to restore normal fecal flora and treat colitis caused by *Clostridium difficile*. Therefore, we proposed that fecal microbial transplantation from a healthy donor could change the fecal flora composition of RMS patients, have a measurable effect on biomarkers of inflammation and possibly influence clinical or MRI disease activity.

We conducted a review about gut microbiome and MS accepted for publication (Mult Scler 2016 Dec 12. Breaking down the gut microbiome composition in multiple sclerosis).

2.2.Description of Fecal Microbial Transplantation

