2.6 Patient population and study rationale

This is essentially an immunological study, and therefore patients with RMS, regardless of the disease duration, will be enrolled in this study. They will be in a standard of care treatment for their MS and may or may not be on treatment with disease modifying therapy as per their own individual case. On the other hand, patients must be off of systemic high dose corticosteroids for at least 90 days.

The primary aim of this study is to determinate if FMT can affect the immunological cytokine profile of MS patients. We also aim to evaluate the safety and tolerability of this treatment in this population. To our knowledge, a study like this has not yet been published anywhere else in the world.

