3.2 Secondary outcomes

We are also aiming to evaluate if FMT can possibly alter gut permeability through urinalysis and peripheral blood DNA bacteria. We also aim to evaluate treatment safety using the Expanded Disability Status Scale (EDSS) and MRI as surrogates for any paradoxical worsening in MS disease activity. We are monitoring adverse events to assess tolerability.

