Unlikely (must have two) In general, this category can be considered applicable to those adverse events which, after careful medical consideration at the time they are evaluated, are judged to be unrelated to the test drug. An adverse event may be considered unlikely if or when:

- It does not follow a reasonable temporal sequence from administration of the test drug.
- It could readily have been produced by the subject's clinical state, environmental or toxic factors, or other modes of therapy administered to the subject.
- It does not follow a known pattern of response to the test drug.
- It does not reappear or worsen when the drug is re-administered.

Possibly (must have two) This category applies to those adverse events for which, after careful medical consideration at the time they are evaluated, a connection with the test drug administration appears unlikely but cannot be ruled out with certainty. An adverse event may be considered possibly related if or when:

- It follows a reasonable temporal sequence from administration of the test drug.
- It could not readily have been produced by the subject's clinical state, environmental or toxic factors, or other modes of therapy administered to the subject.
- It follows a known pattern of response to the test drug.

- Probably** (must have three) This category applies to those adverse events for which, after careful medical consideration at the time they are evaluated, are felt with a high degree of certainty to be related to the test drug. An adverse event may be considered probably related if or when:
- It follows a reasonable temporal sequence from administration of the test drug.
 - It could not be reasonably explained by the known characteristics of the subject's clinical state, environmental or toxic factors, or any other modes of therapy administered to the subject.
 - It disappears or decreases on cessation or reduction in dose. There are important exceptions when an adverse event does not disappear upon discontinuation of the drug, yet drug-relatedness clearly exists (e.g. bone marrow depression, fixed drug eruptions, tardive dyskinesia).
 - It follows a known pattern of response to the test drug.

- Definitely** (must have all) This category applies to those adverse events which, the Investigator feels are incontrovertibly related to test drug. An adverse event may be assigned an attribution of definitely related if or when:

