8.4 Reporting of a serious adverse event

In the event of a SAE, regardless of any opinions on relationship to the study drug, the Medical Monitor is to be notified. In the event that the Medical Monitor cannot be reached, other personnel will be available to receive the report.

All SAEs that are unexpected (i.e., not identified in nature, severity, or frequency in the current Investigator’s Brochure), whether considered to be drug related or not, require a SAE Report Form be completed. All SUSARS (suspected unexpected serious adverse events) must be reported in writing to the Concerned Research Ethics Board (REB).

A death occurring during the study or which comes to the attention of the Investigator within 30 days after discontinuation of study drug, whether considered treatment related or not, must be reported.

Preliminary reports of SAEs will be followed by detailed descriptions which will include copies of the hospital case reports, autopsy reports, and other documents as requested and applicable.

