9.4 Safety Analysis

Adverse events will be coded using MedDRA dictionary. Incidence of adverse events by the severity, relationship to treatment, and outcome will be provided. Narratives of all serious adverse events and events causing death will be included. Laboratory parameters, vital signs and other safety parameters will be documented with the use of descriptive statistics.

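### The causality counts in 8.2.2 will normally hold MS worsening after FMT at 'unlikely' or 'not related', and 9.4 states no split of adverse events by group or period that would make up for it

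*Combined protocol and SAP*

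**What the plan says.** Section 8.2.2 has the investigator rate causality in five categories. 'Not related' is a matter of judgement and names disease among the extraneous causes. The other four work by counts: 'unlikely' needs two of four features, 'possibly' two of three, 'probably' three of four, and 'definitely' all four.

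The 'unlikely' list opens with permissive wording, "An adverse event may be considered unlikely if or when", and includes "It could readily have been produced by the subject's clinical state" and the absence of a known pattern of response. The 'possibly' list reverses both: "It could not readily have been produced by the subject's clinical state", and a known pattern is present. In prose, 'possibly' is described as a link that looks improbable but cannot be excluded.

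On the disease, section 2 says "Relapsing forms of MS (RMS) are generally characterized by clearly defined periods of worsening neurological symptoms". On prior experience, section 2.6 says that to the authors' knowledge "a study like this has not yet been published anywhere else in the world".

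On the use of safety data, section 3.2 names EDSS and MRI "as surrogates for any paradoxical worsening in MS disease activity" and gives adverse-event monitoring the task of assessing tolerability. Section 9.4 plans: "Incidence of adverse events by the severity, relationship to treatment, and outcome will be provided". It states no split by randomised group or by treatment period.

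**The concern.** The event of most interest for harm in this population, a worsening of MS, is also what the underlying disease produces. A rule that counts a plausible disease explanation against relatedness, and also counts the lack of prior experience against it, can settle the rating before timing, improvement on stopping or recurrence are considered. Those are the features that would help to separate an FMT effect from background disease.

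Safety is a secondary objective. Clinical relapse is not a listed outcome in 3.2 or 7.0 and has no row of its own in Tables 1 and 2, so it would be recorded as such only as an adverse event. If the relationship column is then read as evidence, a report could state that no FMT-related MS worsening occurred, and that statement would look much the same with no harm and with substantial harm.

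**Working it through.** The plan gives no figure to reproduce. The check is to apply the counts in 8.2.2 to every combination of five yes/no (1/0) facts:

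- T: timing is reasonable
- C: the clinical state could readily have produced the event
- K: it fits a known pattern of response
- D: it improves on stopping
- R: it reappears or worsens on re-administration

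The rules become:

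- Unlikely: (1−T) + C + (1−K) + (1−R) ≥ 2
- Possibly: T + (1−C) + K ≥ 2
- Probably: T + (1−C) + D + K ≥ 3
- Definitely: T = 1, C = 0, K = 1, and D = R = 1

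'Not related' is left out because it has no count. The 'probably' and 'definitely' lists ask whether the clinical state could reasonably explain the event; this is treated as the same fact as C.

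**Usual MS relapse: C = 1, K = 0.** C = 1 because relapse characterises the population (section 2). K = 0 because the documents describe no MS worsening after FMT; the three MS patients in 2.3 were reported to have improved.

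- Unlikely: (1−T) + 1 + 1 + (1−R) is at least 2 always.
- Possibly: T + 0 + 0 is at most 1, against 2 needed.
- Probably: T + 0 + D + 0 is at most 2, against 3 needed.
- Definitely: fails on C and on K.

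**Other answers to C and K.** With C = 0 and K = 0, possibly = T + 1, met when T = 1, and probably = T + 1 + D, met when T = D = 1. With C = 1 and K = 1 the sums are the same.

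Number of the 8 combinations of T, D and R that meet each category (a combination can meet more than one):

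| C | K | Unlikely | Possibly | Probably | Definitely |
|---|---|---|---|---|---|
| 1 | 0 | 8 | 0 | 0 | 0 |
| 0 | 0 | 6 | 4 | 2 | 0 |
| 1 | 1 | 6 | 4 | 2 | 0 |
| 0 | 1 | 2 | 8 | 6 | 1 |

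In the first row, even good timing with improvement on stopping and recurrence on re-administration (T = D = R = 1) scores 1 of 3 for 'possibly' and 2 of 4 for 'probably'. An event with that history cannot be excluded as FMT-related, which is how the prose defines 'possibly', yet the count bars it from that category. The count and the description disagree.

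These are counts of patterns, not probabilities. They show what the rule permits, not how often each pattern will occur.

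**The case against.** A reader might infer that every MS worsening must be classed 'unlikely'. The documents do not support that. Section 8.2.2 calls the criteria guidelines and leaves the answers to medical judgement, and 'not related' is open too. C is a judgement about the individual patient, so a worsening out of keeping with a stable course could be C = 0. K is not settled for all time either: section 2.7 describes an ulcerative colitis flare after FMT in a patient quiescent for over 20 years, and lists relapse of inflammatory bowel disease (7/1089) among serious events. An investigator who took these as a pattern would set K = 1. All of this stands and makes the block conditional. The permissive wording of 'unlikely' alone does not lift it, because the obstacle lies in the counts that the higher categories require.

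A reader might also infer that the trial has no means of seeing paradoxical worsening. That does not follow. EDSS is scheduled at baseline and months 1 to 12 in both groups and MRI at baseline, 6 and 12 months, with a synopsis rule of 5 or more newly enhancing lesions. None of these needs a causality rating. Nor do the events disappear: all adverse events are recorded whatever their cause, they appear by severity and outcome, and serious ones get narratives.

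Finally, section 8.4 says "All SUSARS (suspected unexpected serious adverse events) must be reported in writing" to the ethics board, which may suggest that serious relapses would go unreported. The section does not define 'suspected' by an 8.2.2 category. It requires notice to the medical monitor for every serious event and a report form for unexpected ones regardless of relationship, and 11.1 sends expedited serious events to the ethics committee.

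What remains is narrower: for MS worsening the relationship column carries little information, and 9.4 states nothing else in the adverse-event tables that links an event to FMT.

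**Conclusion.** The point holds in conditional form. While the investigator judges that the patient's MS could readily explain the event and that no known FMT pattern exists, 0 of 8 combinations of the remaining facts reach 'possibly' or above. If either judgement is reversed, 4 of 8 reach 'possibly' and 2 of 8 'probably'. The first situation will be the normal one at the start of this trial, given sections 2 and 2.6.

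The result assumes that 'readily produced' and 'reasonably explained' are answered alike. If they were answered differently for one event, 'probably' would need T + 1 + D = 3, so 2 of 8 combinations would reach it while 'possibly' stayed closed.

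The consequence is for interpretation, not for data capture or for EDSS and MRI monitoring. As 9.4 is written, the relationship column cannot support a conclusion that FMT caused no MS worsening, and no between-group or between-period table of adverse events is stated that could. Section 8.2.1 adds to the gap: its opening sentence covers participation in the trial, but its listed conditions are tied to the start of study treatment, so relapses in the late group during months 0 to 6 are not clearly counted.

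**What to change.** **In 9.4:** report MS relapses, EDSS worsening and newly enhancing lesions regardless of investigator attribution, by randomised group for months 0 to 6 and by FMT and non-FMT period. The months 0 to 6 table is the randomised comparison. Show the early group's months 6 to 12 on a separate row, since section 6.2.5 treats the time to revert to the original microbiota as an open question. State that the relationship column will not be used to conclude that no FMT-related MS worsening occurred.

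**In 8.2.1 or 9.4:** state that adverse events count from randomisation in both groups.

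**In 8.2.2:** reconcile the count for 'possibly' with its description for events that the underlying MS could also explain. Timing alone should not decide. With monthly enemas over six months, most relapses in that period would have a plausible time sequence, and the column would go from almost none to almost all 'possibly related', with or without an FMT effect.

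**Cost:** one or two extra descriptive tables, a few sentences of protocol text, and a safety summary that may look less favourable. No new assessment or visit is needed.

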8.2.3 Definition of a Serious Adverse Event

Adverse events that are to be considered serious include the following:

- Death, regardless of cause, which occurs within 30 days of the last dose of study drug or if after 30 days is a result of delayed toxicity due to administration of the study drug.
- Immediately life-threatening AE
- Permanently disabling event.
- Hospitalization or prolonged hospitalization excluding those for protocol-specific procedures.
- Congenital anomaly.

“Life threatening” means that the study participant was, in the opinion of the Investigator, at immediate risk of death from the reaction as it occurred. Any other event thought by the Investigator to be serious should also be reported.

The term “severe” is used to grade intensity and is not synonymous with the term “serious”.

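### The only disability criterion for a serious adverse event is permanence, so a disabling MS relapse that recovers without admission is serious only if the open-label investigator calls it so

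*Combined protocol and SAP*

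**What the plan says.** Section 8.2.3 opens its list with "Adverse events that are to be considered serious include the following". The criteria are death, an immediate threat to life, "Permanently disabling event", admission or a prolonged stay (other than for protocol procedures), and congenital anomaly. A closing sentence adds: "Any other event thought by the Investigator to be serious should also be reported".

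Section 2 describes relapsing MS by "clearly defined periods of worsening neurological symptoms [i.e. relapse] followed by full or partial recovery". Section 3.2 uses EDSS and MRI as "surrogates for any paradoxical worsening in MS disease activity".

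On reporting, section 8.4 has the Medical Monitor notified of every SAE. The form is narrower. It is limited to SAEs that the brochure does not already describe, and these, "whether considered to be drug related or not, require a SAE Report Form be completed". Section 9.4 then states: "Narratives of all serious adverse events and events causing death will be included".

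**The concern.** The harm that the trial says it is watching for is MS worsening after FMT. By the protocol's own account a relapse usually recovers at least in part, so a criterion of permanence does not fit the typical case. Permanence also cannot be known when the event should be reported.

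What is at stake is classification. Safety is a secondary objective, there are 20 patients per group, and section 2.6 says that the authors know of no published study like this one. A few disabling relapses classed as serious or non-serious according to one unblinded opinion could change how the safety result reads.

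The form rule raises a smaller issue. Narratives are promised for all SAEs, but the standard document is required for only some of them.

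**Working it through.** No sample size, power or error rate is at stake, so there is no design figure to reproduce. The check traces events through sections 8.2.1 to 9.4.

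**A. A relapse that disables for some weeks, then recovers, without admission**
1. *Adverse event?* Yes. Section 8.2.1 covers new or worsened conditions, including disease progression, and section 8.2.2 sends all adverse events to the case report form (CRF).
2. *Serious by a listed criterion?* No. It is not fatal, not immediately life-threatening, not permanent, not an admission and not a congenital anomaly.
3. *Serious by another route?* Only through the catch-all sentence, which depends on the investigator's opinion. The trial is open label.
4. *Does severity grading mark it out?* Not reliably. In section 8.2.2 the moderate grade specifies no sequelae and the severe grade specifies sequelae needing prolonged intervention. Full recovery points to moderate, while interference with daily activities can point to severe.
5. *Does other monitoring make it serious?* No. EDSS is scored at every visit (Tables 1 and 2), but the text reviewed defines no EDSS change as an event. The one numerical rule for worsening, in the Synopsis, is five or more newly enhancing lesions on MRI, done at baseline, 6 and 12 months.
6. *Narrative under section 9.4?* Only if step 3 made it serious.

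**B. The same relapse with admission.** It is an SAE by the hospitalization criterion and gets a narrative. There is no gap.

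**C. An SAE that the Investigator's Brochure already lists**
1. *Serious?* Yes. Expectedness plays no part in section 8.2.3.
2. *Recorded?* Yes. It enters the CRF as an adverse event, the Medical Monitor is notified, and section 8.4 calls for detailed follow-up descriptions without an expectedness limit.
3. *SAE Report Form?* Not required.
4. *Narrative?* Yes under section 9.4, which does not name the form as its source. No other standard source document is named either.

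**Is C a practical matter?** The systematic review cited in section 2.7 gives SAE rates of 40/659 = 6.1% for the lower route and 9.2% of patients overall. If these applied to the 40 patients:
- At 6.1%: 40 × 0.061 = 2.4 patients expected; P(at least one) = 1 − (1 − 40/659)^40 = 0.92.
- At 9.2%: 40 × 0.092 = 3.7 patients expected; P(at least one) = 1 − (1 − 0.092)^40 = 0.98.

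These rates come from other populations. They show that some SAE is likely, not that any would go unrecorded.

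**The case against.** The list in section 8.2.3 is open, admission counts on its own, and the catch-all lets the investigator report anything else. MS worsening is followed separately by EDSS at every visit and by scheduled MRI. A relapse left non-serious is still tabulated under section 9.4 by severity, relationship and outcome. The proposed wording also still relies on the same unblinded investigator.

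Most of this stands, and it sets the limits of the point. The gap covers only relapses without admission that the investigator does not judge serious. Such a relapse would be visible in the tables; what it would lack is serious status and a narrative. The fix does not remove judgement, but it gives the investigator a stated criterion that can be applied at onset, in place of an unguided opinion.

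A reader might go further and infer that serious harms already known for FMT drop out of the SAE record, or that the SAE listing and narratives could be empty for them. The documents do not support this. As case C shows, expected SAEs remain SAEs, and deaths carry their own reporting duty in section 8.4. Which harms count as expected cannot be settled here, because the brochure is not among the documents. Section 5.5 says that no complications were documented in medically stable patients, while section 2.7 cites serious ones.

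**Conclusion.** The point holds in a limited form. The disability criterion in section 8.2.3 omits significant temporary incapacity, and so leaves a disabling, recovering, non-admitted relapse to be classified by open-label judgement. The mismatch between sections 8.4 and 9.4 is a supporting point about documentation: a mandated form is missing for expected SAEs, but the record is not.

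The size of the gap is unknown. Two calculations that a reader might try do not measure it:
- *Counting relapses.* The documents give no relapse rate. An assumed 0.2 to 0.5 per patient-year over 40 patient-years gives 8 to 20. That counts all relapses, not disabling and non-admitted ones, and it includes 20 × 0.5 = 10 patient-years before the late group receives any FMT. The remaining 30 patient-years give 6 to 15, which still counts every relapse.
- *Share of SAEs of a known kind.* Adding the four kinds named in section 2.7 gives (38 + 27 + 7 + 10)/1089 = 7.5%, and 7.5/9.2 is about 80%. But 38 of these are deaths, which must be reported anyway; without them 44/1089 = 4.0%, and 4.0/9.2 is about 44%. Even that includes relapse of inflammatory bowel disease, although chronic intestinal disease is an exclusion. It also divides a sum over event kinds by a percentage of patients, and presumes that the brochure lists each kind.

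The conclusion therefore rests on the wording of the sections, not on a count.

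**What to change.** 1. In section 8.2.3, replace the permanence criterion with *persistent or significant disability or incapacity*, judged when the event occurs and without waiting to see whether it becomes permanent.
2. In section 8.4, require a SAE Report Form for every SAE, and keep expectedness only as the test for expedited reporting to the ethics board. The section 9.4 narratives then have one standard source.

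The cost is two wording changes in a protocol amendment and a few more forms. At the cited rates about 2.4 to 3.7 of the 40 patients would have any SAE, and only the expected ones among these would need an added form. Disabling relapses newly classed as serious would come on top, in a number that the documents do not allow to be estimated.
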